13.3 Unsolicited Adverse Events

The first-line analysis will use unsolicited adverse event data from all reporting sources combined. A second-line analysis will encompass the analysis of unsolicited adverse events by source.

All the unsolicited adverse events occurring during the study, judged either as probably related, possibly related, or not related to vaccination by the investigator, will be recorded. The original verbatim terms used by investigators to identify adverse events in the case report forms (CRFs) will be mapped to preferred terms using the MedDRA dictionary. The unsolicited adverse events will then be grouped by MedDRA preferred

terms into frequency tables according to system organ class. Adverse events judged by the investigator as at least possibly related to study vaccine will be summarized by vaccine group, according to system organ class and preferred term within system organ class. When an unsolicited adverse event occurs more than once for a subject, the maximal severity and strongest relationship to the vaccine group will be counted.

Only vaccine-emergent adverse events (see [protocol section 8.7](#) for definition) will be analyzed, i.e., excluding those after a subject has given informed consent but before vaccination. The selection of unsolicited adverse events and the assignment to time intervals will be done by day of onset and not by days ongoing/persisting.

The summaries will be presented by period of onset and will include frequency distributions of the different adverse events:

Previously vaccinated subjects:

- Onset between Day 1 and Day 22
- Onset between Day 23 and Day 181

Not previously vaccinated subjects:

- Onset between Day 1 and Day 50
- Onset between Day 51 and Day 209

The analysis of unsolicited adverse events comprises the following categories:

- Any unsolicited adverse event
- Possibly or probably related unsolicited adverse events
- Unsolicited adverse events leading to death
- Serious adverse events
- Possibly or probably related serious adverse event
- Unsolicited adverse events leading to premature withdrawal from study
- Unsolicited adverse events leading to dose reduction, interruption or delay in study vaccination
- Medically attended adverse events

- Unsolicited adverse events leading to new onset of chronic disease (NOCD)

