5.3.2 Safety Follow-up Calls

Safety follow-up calls will be performed on Days 91 and 181, or end of influenza season whichever is longer ("previously vaccinated" subjects) or Days 120 and 209, or end of influenza season whichever is longer ("not previously vaccinated" subjects).

Safety follow-up calls are calls made to the subject by a blinded healthcare professional designated on the site log. These calls will follow a script which will facilitate the collection of relevant safety information. The subject/subject's parent(s)/legal guardian(s) will be interviewed according to the script. Safety follow-up calls performed on Days 91 and 181, or end of influenza season whichever is longer ("previously vaccinated" subjects) or Days 120 and 209, or end of influenza season whichever is longer ("not previously vaccinated" subjects) will collect information relating to a subset of unsolicited adverse events including SAEs, AEs leading to withdrawal, new onset of

chronic disease (NOCD), ILI and concomitant medications or vaccinations associated with those events. All safety information described by the subject must be written down in a designated location within the source document and not written on the script used for the telephone call.

The subject will be asked as to whether he or she was hospitalized or was evaluated at an emergency room for any illness since the site's last contact with the subject. If an SAE has been identified by the site staff during the interview which has not previously been reported by the subject, this SAE will be reported by the site within 24 hours to Seqirus or delegate. Any additional relevant medical history will be reported to Seqirus or delegate and recorded as needed.

ILI assessments will be performed to determine if symptoms of ILI are present. If the subject reports during phone contact that a medical event has occurred with symptoms consistent with an ILI, the subject will be asked to visit the site for further evaluation and potential NP swab taking. An NP swab for evaluation of the presence of influenza virus should be collected as soon as possible, preferably within 3 days, but up to 6 days following onset of protocol defined ILI symptoms (see [Section 5.4.1](#)).

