5.4 Unscheduled Visits

5.4.1 Subjects Meeting the Influenza-Like-Illness Criteria

Clinic Visit or Home Visit – Obtaining NP Swab

Subjects will be asked to come to the site for an unscheduled clinic visit when experiencing symptoms meeting the primary protocol-defined ILI criteria. Subjects will be reminded to bring their ILI booklet. In the exceptional case that a clinic visit is not feasible, a home visit may be considered. The visit should occur as soon as possible, preferably within 3 days, and up to 6 days following onset of protocol defined ILI symptoms. During the visit the following procedures should be carried out:

- Assess ILI symptoms and assess associated medication. Document any anti-viral medication use from the first day of onset of ILI symptoms.
- Collect a NP swab for evaluation of the presence of influenza virus following the procedures for collecting, processing and shipping as described in the Lab Manual.
- Evaluate the subject's body temperature (preferably oral), heart rate, respiratory rate and blood pressure and perform a symptom-directed physical examination.
- Record the ILI, related information, medically-attended adverse events from ILI onset and associated concomitant medication in the source documents and in the eCRF (ILI-report and adverse events section).
- Schedule in next study activity and hand out new ILI booklet.

ILI Follow-up Safety Call

An ILI follow-up safety call will be performed at 30 (+7) days after primary protocol-defined ILI onset, amongst subjects who have had their NP swab obtained

During the visit the following procedures should be carried out:

- Assess ILI symptoms and associated medication, if any.
- Assess for medically-attended adverse event.
- Remind subject of next study activity.

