5.5 Study Termination Visit

The study termination phone call will occur on Day 181 (“previously vaccinated” subjects) or Day 209 (“not previously vaccinated” subjects, or until the end of influenza season, whichever is longer). The termination visit consists of a telephone call. The date of termination is the date of the last contact (telephone call) in which the subject’s health status was assessed or, in cases where the subject and/or parent/legal guardian does not agree to any further safety follow-up, it is the date consent is withdrawn. This date should be recorded on the termination CRF page. For visit procedures to be performed for a subject whose planned study participation ends prematurely, please see [Section 5.5.1, Early Termination Visit](#).

At the termination phone call, the following procedures will be performed:

- Interview the subject to obtain information regarding potential SAEs, ILIs, NOCDs, AEs leading to withdrawal and the medication to treat these.
- Ask the subject or parent/legal guardian as to whether the subject was hospitalized or was evaluated at an emergency room for any illness since the site’s last contact with the subject. If an SAE has been identified by the site staff during the interview and has not previously been reported by the subject, this SAE must be reported by the site within 24 hours to Seqirus or delegate. Record any additional relevant medical history as needed.

Potential ILI symptoms will be documented in the subject’s source records. If the onset of the ILI is 3, or at most 6, days before the visit, an NP swab should be collected from the subject for influenza testing and study staff will document the ILI on an Adverse Event and ILI CRF. See procedures described in [Section 5.4.1](#). Should an ILI be identified, it is recommended to postpone the study termination visit, to allow for the ILI follow-up visit to occur.

- Should the subject have experienced a protocol defined ILI for which an NP swab was obtained, please ensure collection and review of the ILI booklet and collect the information of any medically-attended adverse events which have occurred within 30 days after the onset of the of ILI.

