8.4.3.1.3 Analysis of Unsolicited Adverse Events

This analysis applies to all adverse events occurring during the study, judged either as probably related, possibly related, or not related to vaccination by the investigator, recorded in AE CRF, with a start date on or after the date of first vaccination. AE starting prior to the first vaccination will only be listed.

The original verbatim terms used by investigators to identify AEs in the CRFs will be mapped to preferred terms using the Medical Dictionary for Regulatory Activities (MedDRA) dictionary. The AEs will then be grouped by MedDRA preferred terms into frequency tables according to system organ class. All reported AEs, as well as AEs judged by the investigator as at least possibly related to study vaccine, will be summarized according to system organ class and preferred term within system organ class. These summaries will be presented by vaccination group and by interval of study observation (Day 1 to Day 22, Day 23 to Day 181 in “previously vaccinated” subjects and Day 1 to Day 50, Day 51 to Day 209 in “not previously vaccinated” subjects). When an AE occurs more than once for a subject, the maximal severity and strongest relationship to the vaccine group will be counted.

Separate summaries will be produced for the following categories:

- SAE;
- Adverse events that are possibly or probably related to vaccine;
- NOCD;
- Adverse event leading to withdrawal;
- Adverse event resulting in death.

Data listings of all adverse events will be provided by subject. In addition, adverse events in the categories above will be provided as listed data.

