- If the number of RT-PCR confirmed influenza cases is greater or equal to 381 (targeted number of cases to be able to evaluate the co-primary objective) and subjects have been enrolled over at least three seasons the study will be unblinded and the final analysis will be performed by the sponsor. If the trial proceeds to the final analysis (upon reaching 381 cases) the boundaries for acceptance or rejection are identical to the assumed type 1 and type 2 errors for the overall design, and the trial stops to either reject or not reject the null hypothesis of the primary objective.

That is, the primary objective, i.e. VE against RT-PCR or culture confirmed influenza A and or B will be assess the one-sided 0.025 alpha level.

In case the DMC states that the observed data provides already the full information level needed for the final test decision, then the final analysis can be done on full alpha level of (2.5 % 1-sided) and no further enrollment is needed. If, however, the decision of the group-sequential test is to continue the study then it is on the DMC to determine the number of subjects needed to be enrolled. The DMC should not be influenced by the individual results of the vaccine groups observed at an interim analysis stage when planning further subjects' accrual or the times of future analysis. Only the overall number of cases is allowed to be used for further planning. The following formula for determination of sample sizes for further enrollment may be used:

$$N_{\text{total}} = (C_{\text{planned}} - C_{\text{observed}}) / [(ER_{\text{QIVc}} + ER_{\text{comp}})/2],$$

where N_{total} denotes the total number of subjects needed for further enrollment, C_{planned} is the overall number of cases needed for the test, i.e. 381 cases, C_{observed} are the at that stage observed number of cases overall, and ER are the respective event rates assumed for each group, i.e., 8.0% for non-influenza comparator group and 4.0% for QIVc.

For the analysis of for efficacy, an error-spending function will be applied to provide statistical stopping rules for efficacy (α -boundaries) for the first interim analysis and second interim analysis, if necessary, based on the information accumulated until that specific interim stage, i.e. based on the accumulated variance of the parameter of interest.

These boundaries will be calculated on a p-value see:

<https://support.sas.com/documentation/onlinedoc/stat/131/seqdesign.pdf>

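### Influenza-like illness is not set apart in the late-interval adverse event tables, so the aggregate any-event and medically attended rows partly measure vaccine efficacy

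*SAP*

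**What the plan says.** **How ILI reaches the adverse event data.** Protocol 3.4.1 lists ILIs under its adverse event heading. Protocol 5.3.2 says the safety calls "will collect information relating to a subset of unsolicited adverse events including SAEs, AEs leading to withdrawal", and the same list goes on to "chronic disease (NOCD), ILI and concomitant medications or vaccinations associated with those events". For an ILI found at the termination contact, Protocol 5.5 says "study staff will document the ILI on an Adverse Event and ILI CRF". For the ILI visit, Protocol 5.4.1 has the illness, medically attended events and associated medication recorded "in the eCRF (ILI-report and adverse events section".

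**How those data are tabulated.** Protocol 8.4.3.1.3 opens with "This analysis applies to all adverse events occurring during the study" and covers adverse event form records starting on or after first vaccination, split at Day 22/23 or Day 50/51. SAP 13.3 keeps the same intervals and says "The first-line analysis will use unsolicited adverse event data from all reporting sources combined". That sentence concerns reporting sources and does not mention ILI; inclusion follows because no section takes ILI out. SAP 13.3 lists nine summary categories, among them any unsolicited event and medically attended events. None isolates ILI or confirmed influenza.

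**Endpoint lists.** The protocol synopsis names ILIs in its third safety endpoint. Protocol 8.1.2.1 and SAP 2.2.6 do not.

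**The concern.** After Day 22 or Day 50 the scheduled collection narrows to serious events, events leading to withdrawal, new chronic disease, ILI, and medically attended events in the 30 days after an ILI. With so few other entries, ILI is likely to supply much of the late any-event row. The trial is designed to show that one component of ILI, confirmed influenza, differs between arms. If the vaccine works, that row is lower for QIVc even when nothing else differs.

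The medically attended row is pushed the same way. Under Protocol 5.4.1 the 30-day follow-up call is made to children swabbed for an ILI, so the arm with more influenza is also watched more closely for such events.

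Safety is read descriptively, so readers will take the direction of a summary row at face value. At stake is whether these two rows can be read as safety comparisons.

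**Working it through.** **Inputs from the documents.** Comparator attack rate 8%. Vaccine efficacy (VE) 50% for the co-primary and 45% for the primary objective (SAP 5), giving QIVc rates of 0.08 × 0.50 = 4.0% and 0.08 × 0.55 = 4.4%. SAP 14.1 gives the same planning rates: "8.0% for non-influenza comparator group and 4.0% for QIVc". Arms of 3,846; dropout about 10% (Protocol synopsis).

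**The plan's own case counts.** 6,350 × (0.08 + 0.04)/2 = 381, as stated. 4,814 × (0.08 + 0.044)/2 = 298.5, stated as 298. Enrolment: 6,350/0.9 = 7,056 and 4,814/0.9 = 5,349, both as stated. So these rates are the ones behind the design.

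**Influenza's contribution, upper end.** If every enrolled child is followed and every case falls in the late interval:
- comparator: 0.08 × 3,846 = 308 children;
- QIVc: 0.04 × 3,846 = 154 (VE 50%) or 0.044 × 3,846 = 169 (VE 45%);
- gap: 154 or 138 children, that is 4.0 or 3.6 points.

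**Effect on the any-event row.** Let q be the rate of other late events, equal in both arms, and n the rate of non-influenza ILI. The documents give neither, so q = 1–10% and n = 0–30% are assumptions. With independence, P(any) = 1 − (1 − p_flu)(1 − n)(1 − q), so the gap is (p_comparator − p_QIVc)(1 − n)(1 − q). With n = 0:

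| VE | q | Comparator | QIVc | Gap (points) |
|---|---|---|---|---|
| 50% | 1% | 8.9% | 5.0% | 4.0 |
| 50% | 5% | 12.6% | 8.8% | 3.8 |
| 50% | 10% | 17.2% | 13.6% | 3.6 |
| 45% | 1% | 8.9% | 5.4% | 3.6 |
| 45% | 5% | 12.6% | 9.2% | 3.4 |
| 45% | 10% | 17.2% | 14.0% | 3.2 |

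With n = 10–30% the gap is 2.5–3.6 points at VE 50% and 2.3–3.2 at VE 45%.

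**What shrinks it.** If the 10% who drop out contribute no cases, the influenza gap becomes 0.9 × 154 = 138 or 0.9 × 138 = 125 children. Efficacy cases start more than 14 days after the last dose, about Day 16 or Day 44, so about a week of them falls in the early interval. Cases can also run past Day 181 or 209 to the end of the season. If a fraction f falls in the late interval, the gap is multiplied by f. With the low-end values together, 0.036 × 0.7 × 0.9 × 0.9 = 2.0 points, before applying f.

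**What the aggregate row cannot show.** The QIVc rate of other events that would level the row is 1 − (1 − p_comparator)(1 − q)/(1 − p_QIVc). At VE 50% this is 5.1% for q = 1% and 13.8% for q = 10%, an excess of 3.8–4.1 points; at VE 45% the excess is 3.4–3.7 points. A doubling of other events from 1% to 2% would display as 8.9% against 1 − 0.96 × 0.98 = 5.9%.

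**Medically attended row.** If a share m of confirmed cases is medically attended, the influenza contribution to the gap is m × 3.6–4.0 points. The documents give no m.

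**The case against.** The strongest reply is that the late any-event row carries little weight. SAP 2.2.6 ends the all-unsolicited-events endpoint at Day 22 or Day 50. After that the endpoints are serious events, withdrawals, new chronic disease and post-ILI medically attended events. Safety has no hypothesis test or success criterion. This stands, and it limits the seriousness of the point.

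A reader might infer that a real excess of late events in QIVc would go unseen. The documents do not support that. Serious events, new chronic disease, withdrawals and deaths each have their own summary, as do vaccine-related events, and there are tables by system organ class and preferred term. Most specific signals would still be visible. The levelling calculation applies to the aggregate rows only.

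A reader might also infer that every ILI is certain to be on the adverse event form. The direct instruction in Protocol 5.5 concerns ILI found at the termination contact. Protocol 5.4.1 can be read as sending the ILI to the ILI report and only the accompanying events to the adverse event section. Protocol 3.8, which asks for medically attended events after an ILI to be reported on the adverse event page too, fits that reading without settling it. Against it, 3.4.1 and 5.3.2 class ILI as an adverse event without qualification.

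SAP 11.1 reports attack rates of confirmed influenza by arm, which gives a rough idea of its share. It does not cover test-negative ILI or the adverse event intervals, and it cannot show which children had another event as well. The second-line analysis by source does not commit to separating ILI. The table shells are not in the documents, so an ILI table may already be planned.

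**Conclusion.** The point holds for two late-interval aggregate rows: any unsolicited event and medically attended events. As written, both partly measure vaccine efficacy. At the plan's rates the any-event row favours QIVc by up to about 3 to 4 points with no difference in other events. The gap is about 2.3 to 3.6 points if 10–30% of each arm also has non-influenza ILI, and lower again with dropout or cases outside the interval. This rests on ILI being entered on the adverse event form as a rule, on assumed rates for other events and non-influenza ILI, and on independence between them. The size for the medically attended row cannot be computed from the documents.

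A further tempting step is to take ILI out of the main tables, including the serious and related rows. The documents do not support it. Protocol-defined ILI is fever plus one respiratory symptom, assessed from Day 1. Removing it could move hospitalised influenza, or febrile illness judged related to vaccination, out of the primary safety display.

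**What to change.** In SAP 13.3:

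1. State whether protocol-defined ILI is recorded as an adverse event, and flag adverse event records linked to the ILI form.
2. Keep the all-inclusive tables first-line, with the serious and related rows unchanged.
3. Add late-interval rows for any unsolicited event and for medically attended events that exclude protocol-defined ILI and confirmed influenza.
4. Report ILI and confirmed influenza by arm for the same intervals.

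The cost is one derived flag and a few extra rows, with no new data and no change to the efficacy analyses. It can be specified before unblinding. The downsides are a slightly longer safety output, and that the added rows are conditioned on a post-randomisation event that the vaccine affects. They should therefore be labelled supplementary.

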7. ASSESSMENTS

7.1 Safety Assessment

The measures of safety used in this study are routine clinical procedures. They include a close vigilance for, and stringent reporting of, selected local and systemic adverse events routinely monitored in vaccine clinical studies as indicators of reactogenicity.

An adverse event (AE) is defined as any untoward medical occurrence in a subject or clinical investigation subject administered a pharmaceutical product at any dose that does not necessarily have to have a causal relationship with this treatment. Therefore, an AE can be any unfavorable and unintended sign (including an abnormal laboratory finding, for example), symptom, or disease temporally associated with the use of an investigational product, whether or not considered related to the investigational product. This definition includes intercurrent illnesses or injuries and exacerbation of pre-existing conditions.

The period of observation for AEs extends from the time the subject signs informed consent until he or she completes the specified safety follow-up period Day 181 (for “previously vaccinated” subjects) or Day 209 (for “not previously vaccinated” subjects), or until the end of influenza season, whichever is longer. AEs occurring after the informed consent form is signed but prior to receiving study vaccine/product will be documented as an AE and recorded within source document. However, any AEs occurring prior to receipt of any study vaccine will be analyzed separately from “treatment emergent” AEs (AEs occurring after administration of the first study vaccine).

Adverse events are collected as either solicited or unsolicited adverse events. Solicited events are derived from organized data collection systems, such as subject diaries or interview.

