2.2.6 Secondary Safety Endpoints

Safety will be assessed by calculating:

¹ Geometric mean ratios (GMRs) measure the ratio in immunogenicity titers *within* subjects.

1. The percentage of subjects with solicited local and systemic adverse events (AEs) for 7 days following vaccination at Day 1 (“previously vaccinated” subjects) or Day 1 and Day 29 (“not previously vaccinated” subjects) in the QIVc group and the non-influenza comparator vaccine group.
2. The percentage of subjects with all unsolicited AEs will be assessed from Day 1 to Day 22 for “previously vaccinated” subjects or Day 1 to Day 50 for “not previously vaccinated” subjects in the QIVc group and in non-influenza comparator vaccine group.
3. Percentage of subjects with SAEs, AEs leading to withdrawal from the study and NOCDs reported during the subject’s entire participation in the study, i.e. from Day 1 to Day 181 (for “previously vaccinated” subjects) or to Day 209 (for “not previously vaccinated” subjects), or until the end of influenza season, whichever is longer, and all medications associated with these events.
4. Percentage of subjects with medically-attended adverse events within 30 days after the first occurrence ILI.

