8.2.1 Safety Data

For unsolicited adverse events, the entire study period will be divided into the following intervals: Day 1 to Day 22, Day 23 to Day 181 in “previously vaccinated” subjects and Day 1 to Day 50, Day 51 to Day 209 in “not previously vaccinated” subjects.

For solicited adverse events, the solicited study period 30 min - Day 7 after each vaccination will be divided into: 30 min and Day 1-7 (without the 30-minute interval).

No imputation of missing solicited or unsolicited AEs will be used. The percentage of subjects with missing solicited AE assessments and missing safety phone calls or safety assessment, including subjects who discontinued the study, will be reported for each time.

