8.6 Derived and Computed Variables

Demographics

Age, if not already provided, will be calculated in years using the following formula:

$$\text{Age (years)} = (\text{Date of Visit 1} - \text{Date of Birth} + 1) / 365.25, \text{ round to smallest integer}$$

Body Mass Index (BMI, kg/m²) will be calculated using the following formula:

$$\text{BMI} = \text{Weight (kg)} / \text{Height}^2 \text{ (m}^2\text{)}$$

Immunogenicity

Values below the limit of quantification (recorded as "< LQ") will be set to half that limit (LQ/2).

Titer greater or equal to a given threshold is defined as binary variable for non-missing values as:

= 1, if the titer is superior or equal to the given threshold

= 0, otherwise

HI antibody titer $\geq 1:40$ is defined as binary variable for subjects with non-missing values as:

= 1, if achieving a HI antibody titer $\geq 1:40$

= 0, otherwise

Seroconversion is defined as binary variable for subjects with non-missing values pre-vaccination and post-vaccination as:

= 1, if seroconverted (defined as the percentage of subjects with either a pre-vaccination HI titer $< 1:10$ and a post-vaccination HI titer $\geq 1:40$ or a pre-vaccination HI titer $\geq 1:10$ and a minimum 4-fold rise in post-vaccination HI antibody titer)

= 0, otherwise

Geometric Mean Titer/Concentration

The GMT will be calculated using the following formula:

$$10^{\left\{ \frac{\sum_{i=1}^n \log_{10}(t_i)}{n} \right\}}$$

where t_1, t_2, \dots, t_n are n observed immunogenicity titers/concentrations.

Geometric Mean Ratio

Geometric mean ratios (GMRs) measure the changes in immunogenicity titers/concentrations *within* subjects.

The GMR will be calculated using the following formula:

$$10^{\left\{ \frac{\sum_{i=1}^n \log_{10}\left(\frac{v_{ij}}{v_{ik}}\right)}{n} \right\}} = 10^{\left\{ \frac{\sum_{i=1}^n \log_{10}(v_{ij}) - \log_{10}(v_{ik})}{n} \right\}}$$

where, for n subjects, v_{ij} and v_{ik} are observed immunogenicity titers/concentrations for subject i at time-points j and k , $j \neq k$.

Duration in the Study

Duration of study per subject based on last phone call defined as Day 181 (for “previously vaccinated” subjects) or Day 209 (for “not previously vaccinated” subjects), or until the end of influenza season, whichever is longer.

Duration in the study is defined in days as:

Last visit date (last visit)^a – Enrollment date (visit 1) + 1

^aor premature discontinuation date (in case of withdrawal from the study)

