13.4 Combined Solicited and Unsolicited Adverse Events

Solicited adverse events continuing beyond Day 7 will be reported as an unsolicited AE by the PI and subsequently coded by MedDRA and combined with the unsolicited adverse events as routinely collected beyond Day 7.

A summary of subjects with all combined solicited and unsolicited adverse events will be provided using preferred MedDRA terms for solicited adverse events.

Out of window solicited and unsolicited adverse events and reason for exclusion of these AEs from the analysis of the safety data will be presented as separate listings.

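### The last onset intervals for unsolicited AEs stop at Day 181/209, but SAEs, NOCDs and AE withdrawals are followed to season end if that is later, so late events have no interval

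*SAP*

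**What the plan says.** **Analysis intervals.** SAP 13.3 presents unsolicited AE summaries by period of onset. The last periods are "Onset between Day 23 and Day 181" (previously vaccinated) and "Onset between Day 51 and Day 209" (not previously vaccinated). The placement rule is: "The selection of unsolicited adverse events and the assignment to time intervals will be done by day of onset". SAP 8.2.1 uses the same intervals and introduces them with the statement that "the entire study period will be divided into the following intervals". Protocol 8.4.3.1.3 has the same closed intervals.

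**Follow-up.** SAP 2.2.6, endpoint 3, covers SAEs, AEs leading to withdrawal and NOCDs over the whole of participation: to Day 181 or Day 209, "or until the end of influenza season, whichever is longer, and all medications associated with these events". Protocol 8.1.2.1 agrees. Protocol 7.1 ("The period of observation for AEs extends from the time the subject signs informed consent until") sets the end of AE observation in the same way. So does SAP 8.6 ("Duration of study per subject based on last phone call defined as Day 181", then Day 209 for two-dose subjects, then the season extension). In protocol Tables 4 and 6 the final safety call also carries the season alternative.

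**Two related places.** SAP 13.4 puts "Out of window solicited and unsolicited adverse events and reason for exclusion of these AEs from the analysis of the safety data" into separate listings but does not define the window. Safety endpoint 3 in the protocol synopsis stops at Day 181/209 with no season extension.

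**The concern.** The follow-up rule has two limits and the later one applies: 180 days after the last vaccination, or the end of the season. The onset intervals carry only the first limit, so they do not divide the whole study period as SAP 8.2.1 says they do.

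An SAE, NOCD or AE withdrawal that starts after Day 181/209 but before season end is collected, is vaccine-emergent under SAP 8.6 (which sets no upper day limit) and belongs to endpoint 3. Under SAP 13.3 it still has no period. Two consequences follow if the text is programmed as written:

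- The by-period tables of SAEs, NOCDs and withdrawals omit late events and do not reconcile with the endpoint.
- The closed intervals are the only day limits given in SAP 13.3, so the undefined rule in SAP 13.4 could be read as excluding late events from the safety analysis.

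General unsolicited AEs are collected only to Day 22 or Day 50. The gap therefore concerns the event types followed to the end of participation, which are the more serious ones.

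**Working it through.** This is calendar arithmetic; no power or sample-size formula applies.

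**Inputs from the documents.** One-dose subjects are vaccinated on Day 1. Two-dose subjects are vaccinated on Day 1 and Day 29. The fixed limit is 180 days after the last vaccination. The season ends at the end of June (Northern Hemisphere, NH) or the end of December (Southern Hemisphere, SH), per the protocol Definitions.

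**Assumed.** Day 1 dates, which the documents do not give; 30 June and 31 December as season ends; a non-leap year.

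**The plan's cut-offs.** 1 + 180 = Day 181 and 29 + 180 = Day 209. The intervals therefore end exactly at the 180-day limit, and the season limit is missing.

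**Uncovered days.** Study day of season end, D = (season end − Day 1) + 1. Uncovered days = max(0, D − 181) for one dose and max(0, D − 209) for two doses. Share = uncovered days / D.

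| Season | Day 1 (assumed) | D | One dose | Two doses |
|---|---|---|---|---|
| NH | 1 Oct | 273 | 273 − 181 = 92 (34%) | 273 − 209 = 64 (23%) |
| NH | 1 Nov | 242 | 61 (25%) | 33 (14%) |
| NH | 1 Dec | 212 | 31 (15%) | 3 (1%) |
| NH | 1 Jan | 181 | 0 | 0 |
| SH | 1 Apr | 275 | 94 (34%) | 66 (24%) |
| SH | 1 May | 245 | 64 (26%) | 36 (15%) |
| SH | 1 Jun | 214 | 33 (15%) | 5 (2%) |

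**Break-even Day 1** (season end minus 180 or 208 days):

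- NH: 1 January (one dose) and 4 December (two doses).
- SH: 4 July (one dose) and 6 June (two doses).

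Every subject with Day 1 before these dates has some uncovered follow-up.

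**After the change.** If the last interval ends at the later of the two limits, uncovered days are 0 in every row.

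**The case against.** The strongest reply is that Day 181/209 is shorthand for the end of participation. SAP 8.2.1 means its intervals to be exhaustive. Protocol Tables 4 and 6 treat Day 181/209 and season end as one final contact, and the synopsis drops the extension in some places while stating it in others. On that reading a qualifier was lost and nobody intends to omit late events. That is the likely cause, but SAP 13.3 places events by numbered day of onset, so the label as written does the excluding.

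Second, late events are not lost to the plan. Endpoint 3 counts them. Protocol 8.4.3.1.3 asks for separate SAE, NOCD, withdrawal and death summaries with no day limit, and for listings of all AEs. SAP 11.3 counts deaths without an interval. This stands and limits the harm. However, protocol 8.4.3.1.3 does not say whether its by-interval rule, stated just before, also governs those summaries. SAP 13.3 names no whole-period table, and the SAP 11.3 deaths are counted on the Efficacy FAS, not the Safety Set.

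Third, reading SAP 13.4 as excluding late SAEs would contradict endpoint 3, so that risk is only a possible misreading. This is fair; the point there is the missing definition. The synopsis mismatch can likewise be resolved from protocol 8.1.2.1 and is a minor clean-up.

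Fourth, the day counts rest on chosen dates, ignore the separate season rule for tropical countries, and say nothing about events. All true. The Day 29 window of ±3 days does not change the table: the label is fixed at Day 209, and even a second dose on Day 32 gives 32 + 180 = Day 212, no later than season end in any row showing a two-dose gap.

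Last, safety is descriptive and has no success criterion. That bears on severity, not on whether the text is wrong.

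**Conclusion.** The concern holds. The onset intervals in SAP 8.2.1, SAP 13.3 and protocol 8.4.3.1.3 are shorter than the follow-up in SAP 2.2.6, SAP 8.6 and protocol 7.1 and 8.1.2.1. Applied literally, the by-period tables would omit late SAEs, NOCDs and AE withdrawals and would not add up to endpoint 3.

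On the assumed dates the uncovered stretch runs from 3 to 92 days for NH subjects starting between 1 October and 1 December, and from 5 to 94 days for SH subjects starting between 1 April and 1 June. It is zero for NH starts from 1 January. The number of affected events cannot be derived from the documents. The table shells are not in them either, so whether any actual table would omit events cannot be confirmed. Efficacy, data collection and SAE reporting to the sponsor are unaffected. This should be corrected before unblinding, so that which late events count is not decided afterwards.

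**What to change.** 1. In SAP 8.2.1, SAP 13.3 and protocol 8.4.3.1.3, end the last interval at Day 181 (or 209) or the season's end, whichever comes later.
2. In SAP 13.3, state that SAEs, deaths, NOCDs and AEs leading to withdrawal are also summarised from Day 1 to the end of participation on the Safety Set, to match endpoint 3 of SAP 2.2.6.
3. In SAP 13.4, define the window, and state that events of these types with onset up to the end of participation fall inside it.
4. As a clean-up, align safety endpoint 3 in the protocol synopsis with protocol 8.1.2.1.

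The cost is wording in three SAP sections and two protocol places, plus a changed interval label in the tables. No new data are needed and the design does not change.
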